Any patients with evidence of study drug related adverse events at follow-up will be reviewed by the Data and Safety Monitoring Committee (DSMC) to review all the supporting evidence. The (DSMC) will consist of at least one anesthesiologist, one surgeon and a statistician not otherwise associated with the trial. Their role will be to review the available evidence provided by the research coordinator for the follow-up of all patients including in-hospital and follow-up study drug related adverse events. The outcomes of interest are listed above and will follow-strict study definitions as outlined. All outcomes will be based on consensus of the DSMC.

There will be an interim analysis performed by the Data and Safety Monitoring Committee. This analysis will be conducted when half of the patients have been enrolled. The final analysis will be conducted once all enrolled patients have reached their follow-up date. All final analysis will take into consideration that an interim analysis was conducted.

In case the study is terminated prematurely, the REB will be notified within 14 days in writing including the reason for the termination. If the termination is related to an emergent safety issue, the notification will be faxed to the REB office or preceded by a telephone call to the Chair or REB Coordinator. The study will be unblinded and all patients having received fibrinogen concentrate will be notified in writing and by direct contact via a telephone call of the study termination as well as

Capital Health

the reason for termination. Patients will also be informed of any emergent safety issues or adverse outcomes. Patients will be instructed on how to proceed in terms of medical care and follow up investigations.

RANDOMIZATION METHOD

Informed consent will be obtained from the patient prior to the operation either in the same-day surgery clinic or at the bedside if the patient has already been admitted to hospital pre-operatively. The randomization process will be performed with the help of software (G*Power version 3.1.2). Treatment allocation cards will be provided by the study Sponsor and placed in sealed, opaque envelopes for safe storage in a secure location to preserve the integrity of the blinding. The study drug designate will withdraw the envelope directing the patient's randomization to the FIB group or the PLACEBO group. Both the surgeon and anaesthesiologist will be blinded to patient randomization.

Randomization process

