As per the standard of care in this surgical population, all post-operative cardiac surgery patients will be taken immediately to a dedicated cardiovascular intensive care unit (CVICU). All patients will receive respiratory and hemodynamic support as needed. Each patient will be required to meet standard hospital criteria both prior to extubation and prior to transfer to the intermediate-care unit (IMCU). Discharged patients will be transferred to an intermediate-care unit or general-care ward under the care of the same cardiac surgical team. All patients will be monitored continuously for a minimum of 24 hours. In case of a post-operative bleeding in CVICU the same algorithm (Figure 3) like in the OR will be used. In case of surgical bleeding a re-sternotomy will be performed. Diffuse bleeding will be treated with blood components (step 2 -5, Figure 3). Patients having a valve replaced with a mechanical valve will receive heparin or warfarin 48 hours after surgery. All other patients will get ASA (acetylsalicylic acid, Aspirin®, Bayer Canada) on the first postoperative day (anticoagulation protocol, Division of Cardiac Surgery, QEII, Halifax, Canada).

ASSESSMENT OF SAFETY

Adverse Events

The following treatment-emergent and adverse effects will be captured during this study from the date ~~the consent was signed~~ of randomization to the 6 month follow-up:

Treatment-emergent adverse events

- Pleural effusion
- Atrial fibrillation
- Postoperative Delirium
- Reoperation because of surgical bleeding and unknown bleeding
- Air embolism

Adverse events (A/E) and Serious adverse events (SAE)

- Anaphylaxis
- Stroke
- Myocardial infarction
- Pulmonary embolism
- Deep vein thromboembolism
- Sternal wound infection
- Recurrent angina
- Angiography
- Percutaneous coronary intervention (PCT)
- Repeated cardiac surgery
- Cardiorespiratory arrest
- Cerebral hemorrhage
- Death

All serious unexpected adverse drug reactions will be reported to Health Canada as per ICH/GCP guidelines.

Unblinding

Unblinding for this study will occur when:

1. Clinical treatment decisions need to be made and when an unexpected serious adverse event occurs and the intervention must be made known.
2. At the request of the Data Safety Monitoring Committee.

Capital Health

3. After 110 participants have reached the primary endpoint for interim analysis.
4. At the conclusion of the study to determine the effect of the intervention.

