The Blood Transfusion Services are able to unblind for the clinical treatment of a patient. Please refer to the site Standard operating procedure for more details of this process. If a patient's treatment is unblinded before the 24 hour primary end point their data will not be used in the analysis.

STATISTICS

Sample size

The primary outcome of interest will be overall need for blood transfusion at 24hr after surgery (including all used blood components from the start of surgery). For the sample size calculations G*Power version 3.1.2 was used.

Based on the available literature ^{9,10,12}, the investigator hypothesized a 70-90% reduction in total units of blood products in the group receiving fibrinogen compared with the group receiving conventional therapy. An estimate of blood product requirement in the group receiving conventional therapy is mean 3.4 units (standard deviation 5.9) based on our data from 2005 to 2007 for AVR+CABG, MVR+CABG, AVR+MVR, and Aortic root repair +/-AVR. Standard deviation 5.9 was used for both groups. Blood product requirement in the two groups will be compared using the Mann-Whitney U test for two independent samples. The sample size calculation was based on a two-tailed test with $\alpha = 0.05$, for $\beta = 0.2, 0.1, \text{ and } 0.05$. The sample sizes shown Table 1 represent the number of patients required in each group.

Details of the planned analysis

~~Individual case forms will be completed by the research coordinator for individual patients.~~ **The research coordinator will complete individual case forms for individual patients.** These forms will be detailing demographic characteristics,

Capital Health

intra-operative, post-operative and follow-up outcomes. Outcome data and blood samples will be collected according a lab/data schedule (Table 2). ~~All data will be reviewed by the appropriate clinical outcomes committee.~~ **The Sponsor will review all data.** Once reviewed all data will entered and maintained electronically.

Primary outcome: Blood component requirement in the two groups will be compared using the Mann-Whitney U test for two independent samples.

Secondary outcomes: Univariate comparisons between patients randomized to FIB and patients randomized to PLACEBO group will be carried out based on pre-, intra-, and post-operative variables using Chi-square tests for dichotomous variables, two-tailed t-tests for continuous variables and Wilcoxon rank sum tests for nominal variables.

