Approximately 200 complex cardiac procedures are performed annually in Halifax by nine cardiac surgeons. Of these patients, conflicting studies and patients being disqualified on the basis of exclusion criteria will result in a maximal annual number of eligible patients of 100 per year. We would plan to recruit 222 patients for this study. With a length of follow up of 6 months and using administrative data of an already well established data base we are expecting a rate of loss under 5%.

DATA HANDLING AND RECORD KEEPING

Data will be collected from patient charts and health records, the anesthetic record as well as the Maritime heart center cardiac surgery database. A data collection sheet will be filled out by the study nurse for patients included in the study. Follow-up data will be collected from patients themselves. In cases where patients have adverse outcomes, this information will be obtained from hospital records and the patient.

A data collection form will be used to collect study information and will be completed by the designated study personnel for participants. These forms will be detailing demographic characteristics, intra-operative, postoperative and follow-up outcomes. Individual data forms will record: the perioperative amount of blood products used (packed red cells, FFP, platelets,

Capital Health

Cryo). Also fibrinogen levels, hematocrit, PTT, INR, platelet count, Hemoglobin, Thromboelastometry (ROTEM®, CT, CFT, Angle, MCF), CVICU-stay, Hospital-stay, In-Hospital Mortality, Hemoglobin, adverse events (anaphylaxis, stroke, myocardial infarction, pulmonary embolism, and deep vein thromboembolism) and usage of factor VII concentrate and human prothrombin complex will be collected for study purposes. All data will be reviewed by the appropriate **outcome** committee. Once reviewed all data will be entered and maintained electronically on a designated CDHA computer.

Data will also be collected using the Maritime Heart Center (MHC) cardiac surgery database. This database is a prospectively collected, clinical database that captures detailed information on a wide range of pre-operative, intra-operative, and in-hospital postoperative variables including post-operative complications and in-hospital mortality for all patients undergoing cardiac surgery at the QE II Health Sciences Center.

QUALITY CONTROL AND QUALITY ASSURANCE PROCEDURES

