Data validation will be an integral part of this protocol and will be carried out using already established clinical and administrative patient databases available through the Division of Cardiac Surgery at the QEIIHSC. This will ensure 100% follow-up of all patients and data accuracy. **The Data and Safety Monitoring Committee will investigate all discrepancies.**

Monitoring

The study will be monitored in accordance with ICH-GCP guidelines that require a minimum of three visits, before the trial starts, once during the trial, and after the trial is completed.

Data Storage

[figure not shown]

Capital Health

During the study data will be stored in a filing cabinet in a designated office for the study nurse as well as a CDHA computer, as a data file. All other data will be stored on the CDHA network. Once the study is complete, data will be stored in a filing cabinet in the Principal investigator's office under lock and key. All other data will be stored as per current standard of practice for elective cardiac surgery patients; on the CDHA network and in the Maritime Heart Center (MHC) cardiac surgery database. De-identified information will be available to the sponsor after study completion. In case of adverse outcomes, the study will be unblinded and may be reviewed by regulatory agencies through CDHA. The research team also intends to publish de-identified in a research journal that will be available to the study participants and to the public.

~~Prior to data transfer to CSL Behring, study participant information will be de-identified using a serial number system. This unique number will be assigned to each study participant and will be stored on paper in a filing cabinet in a designated, secure office in the Department of Anesthesia.~~ The study research data will be archived for a minimum of 25 years according to the current Capital Health policy. Once the information requires destruction, paper data will be shredded through the hospital confidential waste disposal. Electronic data will be deleted from the designated CDHA computer. Data stored independently on the CDHA hospital network and the Maritime Heart Center database will be disposed of by the regulations governing those networks or databases.

Figure 1. ROTEM® Parameters

CT (clotting time): time from start of measurement until initiation of clotting
 => initiation of clotting, thrombin formation, start of clot polymerisation

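### The Data Storage section unblinds the whole study on any adverse outcome, a trigger that conflicts with the Unblinding list and the premature-termination rule

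*Combined protocol and SAP*

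**What the plan says.** Five places in the protocol bear on when the blind is broken.

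- **Data Storage** (under Quality Control and Quality Assurance Procedures): "In case of adverse outcomes, the study will be unblinded and may be reviewed by regulatory agencies through CDHA". The sentence is current text, and adverse outcomes are not defined.
- **Unblinding** (under Assessment of Safety) lists four occasions. The first is "Clinical treatment decisions need to be made and when an unexpected serious adverse event occurs and the intervention must be made known". The others are "At the request of the Data Safety Monitoring Committee", "After 110 participants have reached the primary endpoint for interim analysis" and "At the conclusion of the study to determine the effect of the intervention". The text after the list adds: "If a patient's treatment is unblinded before the 24 hour primary end point their data will not be used in the analysis".
- **Methodology**, paragraph on premature termination: "The study will be unblinded and all patients having received fibrinogen concentrate will be notified in writing". The same section sends adverse events related to the study drug to the DSMC for review and does not mention unblinding for them.
- **Subject withdrawal criteria** unblind an individual patient whose FIBTEM amplitude exceeds 20 mm. The Unblinding list does not name this occasion.
- **Data Handling and Record Keeping** uses the phrase adverse outcomes for events in individual patients: "In cases where patients have adverse outcomes, this information will be obtained from hospital records and the patient".

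**The concern.** The Data Storage sentence makes an undefined event the trigger and the study, not the participant, the thing unblinded. The Adverse Events section plans to capture stroke, myocardial infarction, pulmonary embolism, repeat cardiac surgery, sternal wound infection and death, from randomization to six months after complex cardiac surgery. Events of this kind are to be expected, so a literal trigger could well be met while patients are still being recruited.

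Three things are at stake.

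1. Follow-up at six weeks, three months and six months relies partly on a clinic visit or telephone interview by a research coordinator. Once arms are known, ascertainment and attribution of events can differ by arm.
2. A patient unblinded inside the 24-hour window is removed from the analysis by the rule quoted above, because of another patient's event.
3. The primary outcome is the amount of blood components transfused, which rests partly on judgement: surgeon and anesthesiologist assess the bleeding and agree when surgical hemostasis is complete. The Randomization Method section requires both to be blinded. Unblinding would show them how treated patients have fared by arm, which could shape later decisions even though the next patient's arm remains concealed.

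**Working it through.** **Step 1. The provisions side by side.**

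| Section | Trigger | What is unblinded |
|---|---|---|
| Data Storage | any adverse outcome | the study |
| Unblinding, item 1 | treatment decision with an unexpected serious event, where the intervention must be known | not stated |
| Unblinding, item 2 | DSMC request | not stated |
| Unblinding, item 3 | 110 participants at the primary endpoint | not stated |
| Unblinding, item 4 | study conclusion | not stated; by context, the study |
| Methodology | premature termination | the study |
| Subject withdrawal criteria | FIBTEM above 20 mm | the patient |

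The first row matches none of the others. Where the protocol means one patient, as in Subject withdrawal criteria and in the 24-hour exclusion rule, it says so. Where it speaks of the study being unblinded, in Methodology, it means the whole trial.

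**Step 2. How likely is the literal trigger to be met?** The plan states no event rate and no probability, so there is no figure of its own to reproduce. The inputs are:

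- n = 110 (Unblinding, item 3) and n = 222 (Estimated Recruitment Rate).
- p, the chance that a patient has at least one qualifying event over full follow-up. This is **assumed** to be 1%, 2% or 5%.
- Patients are taken as independent, so P(at least one event) = 1 − (1 − p)^n.

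For n = 110:
- p = 1%: 1 − 0.99^110 = 1 − 0.331 = 67%
- p = 2%: 1 − 0.98^110 = 1 − 0.108 = 89%
- p = 5%: 1 − 0.95^110 = 1 − 0.0035 = 99.6%

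For n = 222 the results are 89%, 99% and about 100%.

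**Step 3. Allowing for timing.** Step 2 credits each patient with the whole six-month risk at enrolment, so it overstates how soon the trigger is met. A cautious bound counts only patients who have finished follow-up. At the maximum of 100 eligible patients a year, 50 enrol in any six months. When patient 110 enrols, 110 − 50 = 60 have completed six months. Then:
- p = 1%: 1 − 0.99^60 = 45%
- p = 2%: 1 − 0.98^60 = 70%
- p = 5%: 1 − 0.95^60 = 95%

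The chance that the trigger has been met when patient 110 enrols lies between these figures and those of Step 2. Recruiting 222 patients at 100 a year takes at least 222/100 = 2.2 years, so most events in early patients would still fall within recruitment.

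**Step 4. A narrow reading.** If adverse outcomes meant only drug-related events, at the upper limit of 1 in 10,000 given under Risks, the chance in 111 treated patients is 1 − 0.9999^111 = about 1%. The sentence does not state that limit.

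**Step 5. How many primary outcomes are exposed directly?** At 100 patients a year, the average number inside a 24-hour window on a given day is 100/365 = 0.27. Patients past 24 hours already have a fixed primary outcome.

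**The case against.** The strongest reply is that the sentence is not an unblinding rule. It stands in a paragraph on record access, between sponsor access after study completion and publication, and its subject may be what regulators can see. Methodology also mentions adverse outcomes in its premature-termination paragraph, so the sentence could be shorthand for that case. The operative rules are under Unblinding, with emergency requests handled by Blood Transfusion Services under a site procedure. This makes a harmless intention plausible. The sentence states none of these limits, however, and a harmless intention is a reason to correct it.

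A second reply concerns the harm, and most of it stands. A reader might infer that every later transfusion decision would be made with the arm known, so that the double blind for the primary endpoint is lost. The documents do not support that. Allocations are held in sealed, opaque, sequential envelopes, opened for each patient in the blood bank by the study drug designate. Disclosing the arms of treated patients does not open unused envelopes. The direct loss of primary data is likely to be about one patient at most on a given day (Step 5).

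A third reply is that the Unblinding list is itself loose. Item 3 already provides for unblinding at 110 participants without saying who learns the allocation, and the list omits the FIBTEM provision. This is correct. It means that several sections need reconciling, but it does not remove the conflict with Data Storage.

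**Conclusion.** The contradiction is established from the text alone. Data Storage gives a study-wide unblinding trigger that the Unblinding list does not contain and that Methodology reserves for premature termination.

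How soon a literal trigger would be met rests on assumed event rates. At 1% to 5% per patient over full follow-up, at least one event among the first 110 patients has a probability of 67% to 99.6%. It would probably be met during recruitment, but the documents do not show that this is certain or when it would happen.

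The damage would be to follow-up and adverse event reporting, to any patient still inside 24 hours, and to clinicians' equipoise through sight of results by arm. It is an inconsistency that should be corrected because the sentence, if obeyed, would harm the blind. It is not evidence that the trial's allocation concealment fails.

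**What to change.** Remove the unblinding clause from Data Storage and replace the sentence with wording such as:

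> Regulators may inspect, through CDHA, the records of participants who have adverse outcomes. An adverse outcome does not by itself unblind the study. Unblinding follows the Unblinding section (including a DSMC request and the interim analysis), the FIBTEM provision under Subject withdrawal criteria, and the premature-termination provision in Methodology.

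The replacement should not simply seal all other allocations until database lock, because that would contradict the DSMC-request and interim items. Nor should it confine disclosure to the Unblinding section alone, because that would leave the FIBTEM provision in doubt.

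In the same amendment, reconcile Methodology, Subject withdrawal criteria, the Unblinding list with the 24-hour exclusion that follows it, and Data Storage. Each should state whether a participant or the study is unblinded, and to whom.

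The cost is one replaced sentence and short clarifications in a protocol amendment. Sample size, power and alpha do not change, and emergency unblinding through Blood Transfusion Services is unaffected.
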